4.0 BACKGROUND AND RATIONALE

4.1 Background

Each year, cigarette smoking accounts for an estimated 438,000 deaths and \$92 billion in productivity losses in the United States (Centers for Disease Control and Prevention, 2005). The prevalence of smoking in illicit drug abusers is 49 – 98%, a rate substantially higher than the 19.8% smoking prevalence in the general population (Schroeder, 2009). A link between cigarette smoking and non-nicotine stimulant abuse has been established in both clinical and laboratory studies. The results from clinical studies suggest that the rate of smoking in cocaine abusers is 75-80% (Budney et al., 1993; Sees and Clark, 1993; Gorelick et al., 1997) and that smoking cigarettes is associated with more severe addiction, including more frequent cocaine use, a greater likelihood of injecting or smoking cocaine, and more severe employment and legal difficulties (Roll et al., 1996). A recent outpatient study in methamphetamine (METH) dependent individuals reported that 65% of the participants were current cigarette smokers (Shoptaw et al., 2008b). Human laboratory studies have found that cocaine administration increases the rate of cigarette smoking (Nemeth-Coslett et al., 1986; Roll et al., 1997) and that mecamylamine, a nicotine antagonist, reduces cue-induced cocaine craving (Reid et al., 1999).

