5.2 Secondary Objectives

1. To evaluate the longer-term impact (through 6-month follow-up) of TAU+SCT, relative to TAU, on stimulant use outcomes in cocaine/METH-dependent individuals in outpatient substance-abuse treatment.

2. To evaluate the initial impact of TAU+SCT, relative to TAU, on other drug-abuse outcomes in cocaine/METH-dependent individuals in outpatient substance-abuse treatment.

3. To evaluate the longer-term impact (through 6-month follow-up) of TAU+SCT, relative to TAU, on other drug-abuse outcomes in cocaine/METH-dependent individuals in outpatient substance-abuse treatment.

4. To evaluate the initial efficacy of TAU+SCT, relative to TAU, in improving smoking outcomes in cocaine/METH-dependent individuals in outpatient substance-abuse treatment.

5. To evaluate the longer-term efficacy (through 6-month follow-up) of TAU+SCT, relative to TAU, in improving smoking outcomes in cocaine/METH-dependent individuals in outpatient substance-abuse treatment.

6. To evaluate whether achieving continuous smoking abstinence during study weeks 6-9 is associated with improved stimulant use outcomes in cocaine/METH-dependent individuals in outpatient substance-abuse treatment.

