In the present study, the smoking quit date will occur during study week 3. A combination of daily self-reported smoking data and weekly CO levels will be used to determine continuous abstinence during postquit days 15 – 42. This time-frame was selected based on the recommendation that a two-week post-quit grace period be included in smoking-cessation studies during which time smokers can smoke without it being counted as a treatment failure (Hughes et al., 2003). The use of a 4-week abstinence period is consistent with FDA standards for approving smoking-cessation medications (Hughes et al., 2003). Continuous abstinence will be defined as no self-reported smoking on any of the days during this four-week period AND no positive CO level (>8 ppm) measurement during the same period AND at least one CO assessment per week. Because a positive CO level almost always indicates smoking on either the day of the measurement or the previous day, smoking during the post-grace period will be indicated by a positive CO level measured on any of the post-quit days 16-42. (A positive value on day 15 might be due to smoking on day 14, which is within the grace period.) In order to have no missing CO week measurements, the following conditions must be met: at least four CO measurements must be obtained during this period; the first one may be no later than post-quit day 23, and no subsequent measurement may fall more than 13 days after the previous measurement.

4. Initial Quit

Achieving an initial quit is defined as a self-report of no smoking for 24 hours or more (Hughes et al., 2003). In the present protocol, if the participant meets this criterion at any time during the first two weeks following the smoking quit date (as determined by TLFB) then s/he will be scored as having achieved an initial quit.

5. Cigarettes per Day (CPD)

The TLFB assessment will be used to evaluate the number of CPD that the participant reports using throughout the study as outlined in Table 2.

6. Non-cigarette Tobacco Use

Participant use of non-cigarette tobacco products will be assessed on the TLFB as outlined in Table 2.

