8.10.2 Nicotine Inhaler

Study participants randomly assigned to the TAU+SCT condition will be prescribed 6-16 nicotine cartridges per day ad libitum starting with the smoking quit date (study day 20) through week 10. During week 10, participants will be provided with a 3 week taper in which a maximum of 12 cartridges per day is taken in the first week, a maximum of 8 cartridges per day is taken in the second week, and a maximum of 4 cartridges per day is taken in the third week.

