 - a lower number of CPD during the prior 28 days at the 3- and 6-month follow-up visits
- 6. Participants who achieve continuous smoking abstinence during post-quit days 15 42, relative to participants who do not, will have better stimulant-use outcomes including:
 - a significantly greater percentage of participants with stimulant-free weeks (see section 6.5.1 for the definition of stimulant-free weeks) during study weeks 4-10 of the active treatment phase;
 - a significantly greater percentage of participants with stimulant-free urines at 3- and 6-month followup visits

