8. Smoking Point-Prevalence Abstinence

GLMM analyses including site and treatment group will be used to model rates of achieving point prevalence abstinence as assessed at the week 10 visit of the active treatment phase and at the 3- and 6- month follow-up visits.

9. Continuous Smoking Abstinence

GLMM analyses including site and treatment group will be used to model rates of achieving continuous smoking abstinence during post-quit days 15-42.

10. Cigarettes per Day (CPD)

Given the smoking quit date's likely substantial impact on CPD, analyses for CPD during the active treatment phase will be conducted for the pre-quit and post-quit phases as well as for the entire treatment phase, with the treatment x week interaction effect for study weeks 4-9 being the effect of interest. A

repeated measures mixed model analysis will be conducted to compare the CPD reported for the 28 days prior to the 3 and 6-month follow-up visits as a function of treatment group.

11. Participants with Continuous Smoking Abstinence

The primary outcome analysis will be modified to compare the percentage of participants who achieve continuous smoking abstinence, relative to those who do not, on stimulant-free weeks during study weeks 4-10 of the active treatment phase. In addition, GLMM analyses will also be conducted to compare the percentage of participants who achieve continuous smoking abstinence, relative to those who do not, on stimulant-free UDS at the 3- and 6-month follow-up visits.

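### Hypothesis 6 compares smoking abstainers with non-abstainers on stimulant use that mostly precedes or coincides with the abstinence window, with no stated adjustment for earlier stimulant use

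*Protocol*

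**What the plan says.** Protocol section 6.5.2.2 item 3 defines the grouping variable: daily self-report and "weekly CO levels will be used to determine continuous abstinence during postquit days 15 – 42". One reported smoking day in that period, or one CO reading above 8 ppm from post-quit day 16 on, ends abstainer status. The first two weeks after the quit date are a grace period in which smoking does not count.

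Section 5.2, objective 6, gives the same window in study weeks. It asks whether "achieving continuous smoking abstinence during study weeks 6-9 is associated with improved stimulant use outcomes".

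Section 11.1.2, hypothesis 6, is directional: abstainers "will have better stimulant-use outcomes including" a significantly greater percentage with stimulant-free weeks in study weeks 4-10. Section 11.3.2 item 11 tests this by modifying the primary analysis to compare the two groups "on stimulant-free weeks during study weeks 4-10 of the active treatment phase". It adds comparisons of the 3- and 6-month urine drug screens (UDS).

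The primary model in section 11.3.1 has treatment, week, their interaction and a random site effect. It has no term for baseline or earlier stimulant use. Sections 11.3.1 and 11.3.2 both say that the interaction with week carries the effect of interest. Section 11.3.4 counts missing smoking or CO data as smoking.

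Section 4.1 reports laboratory findings that "cocaine administration increases the rate of cigarette smoking".

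**The concern.** Abstainer status is not settled until week 9, yet it is used to explain stimulant use from week 4 on. Section 4.1 supplies a pathway in the opposite direction: a stimulant relapse in weeks 6-9 can make a participant smoke, which places that participant in the non-abstinent group and at the same time produces the stimulant-positive weeks counted against that group. Stimulant use is also strongly correlated within a person over time, so the groups would differ in weeks outside the window too.

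What is at stake is the answer to objective 6. A significant difference could be read as a benefit of quitting when it reflects who was able to quit.

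**Working it through.** The protocol gives no computed figure for this comparison, so there is none to reproduce. The check has two parts.

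**1. Time order.** Section 8.10.2 puts the quit date on study day 20 ("starting with the smoking quit date (study day 20) through week 10"); section 6.1 puts it at the end of week 3, which is day 21 at the latest.

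- Quit day 20: post-quit days 15-42 are study days 20 + 15 = 35 to 20 + 42 = 62.
- Quit day 21: study days 36 to 63.
- Week 5 ends on day 35 and week 9 on day 63, so the window is weeks 6-9, give or take a day.

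| Outcome weeks | Position relative to abstinence window | Count |
|---|---|---|
| 4-5 | before | 2 |
| 6-9 | during | 4 |
| 10 | after | 1 |

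Six of seven outcome weeks (6/7 = 86%) do not follow the exposure. Weeks 4-5 also fall in the grace period, so a participant later classed as abstinent may still be smoking then.

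**2. Size under no effect of quitting (simulation).** Assumed inputs:

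- Stimulant-free rate 65%, the midpoint of the 0.6 and 0.7 in section 11.4.
- A latent Gaussian process with a random-intercept share of 0.60 and autoregression of 0.80, which gives a lag-1 correlation of about 0.74.
- A weekly chance of smoking abstinence of 0.92 for 30% of people and 0.15 for the rest, multiplied by 1.0, 0.8 or 0.5 in a stimulant-use week.
- Abstinence requires all of weeks 6-9 and never alters stimulant use.

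The odds ratio (OR) is [p1/(1-p1)] / [p0/(1-p0)], abstainers over non-abstainers. For weeks 4-10:

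- Multiplier 0.8: 77.4% v 62.6%, so (0.774/0.226)/(0.626/0.374) = 3.42/1.67 = 2.0.
- Multiplier 0.5: 90.4% v 61.2%, so (0.904/0.096)/(0.612/0.388) = 9.42/1.58 = 6.0.

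| Comparison, true effect none | No link | 20% lower | 50% lower |
|---|---|---|---|
| Weeks 4-10, unadjusted | 1.0 | 2.0 | 6.0 |
| Weeks 4-5 only (before the window) | 1.0 | 1.8 | 4.2 |
| Week 10 only, unadjusted | 1.0 | 1.9 | 4.7 |
| Week 10, adjusted for weeks 1-3 | 1.0 | 1.6 | 3.2 |
| Week 10, adjusted for weeks 1-9 | 1.0 | 1.0 | 1.0 |

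Repeat runs move the larger entries by 0.1 to 0.2.

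A second set of simulations used the correlation of 0.65 from section 11.4 and different assumed abstinence probabilities (0.75 in stimulant-free weeks; 0.60, 0.45 or 0.30 in stimulant-use weeks):

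- Compound symmetry: weeks 4-10 OR 2.2, 4.7 and 10.3; week 10 only 2.1, 4.1 and 7.6.
- Lag-1 dependence: weeks 4-10 OR 1.8, 2.9 and 4.7; week 10 only 1.5, 2.2 and 3.0.
- Week 10 adjusted for earlier stimulant status: 0.97 to 1.03 throughout.

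**Which parameter is tested.** In simulated trials of 528 under the first set of assumptions, a level test wrongly favours abstainers in 92-94% (multiplier 0.8) and 100% (0.5). A positive abstinence-by-week interaction is significant in only 5.0% and 11.8%, against a nominal 2.5%.

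**Cost of full adjustment.** With an assumed real post-quit effect, adjusting for weeks 1-9 shrank the OR from 1.57 to 1.29.

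**The case against.** The case against has several parts, and much of it stands.

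- **Objective 6 asks only about association.** True, and an unadjusted comparison can describe one. But the objective speaks of improved outcomes and hypothesis 6 predicts better ones, which invites a reading in terms of benefit.
- **The named parameter is the interaction with week.** A reader might infer that the trial would almost always declare a false benefit. The documents do not support that. Item 11 does not say which parameter carries over, and the inflation is small for the interaction. Hypothesis 6, however, is worded as a greater percentage, so a level test is a natural reading.
- **The overlap of windows is not the main driver.** A reader might infer that moving the outcome to after week 9 cures the problem. It does not: week 10 alone still gives 1.9 to 4.7. The unadjusted comparison of self-selected groups matters more. The 3- and 6-month comparisons are correctly ordered but have no stated adjustment for earlier stimulant use either.
- **The covariates may be settled elsewhere.** Item 11 says only that the primary analysis will be modified, and section 11.3.4 adds baseline covariates related to missingness. It cannot be claimed that treatment arm is left out. The outcome window and the group comparison, though, are fixed in the protocol itself.
- **The link strengths are assumptions.** Section 4.1 supports the direction, not the size. The first simulation implies 13-21% abstinent across both arms, while section 4.2.2 cites 11% during active treatment in an earlier trial. Fewer abstainers would lower the share of false-positive trials.

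**Conclusion.** The concern holds in this form: as written, a level comparison under hypothesis 6 cannot separate an effect of quitting on stimulant use from an effect of stimulant use on quitting. With no true effect it gives an illustrative OR of 2.0 to 6.0 over weeks 4-10, if a stimulant-use week lowers that week's chance of abstinence by 20% to 50%. These figures show direction and range, not the bias to expect in this trial.

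Counting missing smoking data as smoking, while section 11.3.1 leaves weeks with no urine sample and no reported use as missing, adds a link through attendance that the simulations do not include.

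It would be wrong to infer that the trial's main conclusion is at risk. The randomized primary comparison does not use smoking status. This is a should-fix for the last of six secondary objectives.

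**What to change.** Before analysis, change hypothesis 6 and item 11 as follows.

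1. Test hypothesis 6 on outcomes after the abstinence window: week 10 and the 3- and 6-month UDS. State that the group coefficient (level), not an interaction with week, is tested.
2. Adjust for treatment arm, site, baseline UDS stratum and pre-quit stimulant status (weeks 1-3). Arm matters because only TAU+SCT participants receive the cessation package.
3. Report a second version that also adjusts for stimulant status through week 9. State what each version can and cannot do. The pre-quit version leaves residual bias (week-10 OR about 1.6 to 3.2 under no effect). The fuller version removes the reverse-causation bias in the simulations but may also remove part of a true effect acting in weeks 4-9.
4. Report weeks 4-9 as a concurrent, descriptive association.
5. Word hypothesis 6 as an association, not as a benefit of quitting.

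All the variables are already collected, so the cost is wording and model specification. The downside is fewer outcome time points and a wider interval. Neither version identifies the causal effect by itself; together they show how far the answer depends on the adjustment.

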11.3.3 Safety Analyses

1. Adverse events

Adverse events (AEs), including serious adverse events (SAEs), will be summarized by body system and preferred term using MedDRA (The Medical Dictionary for Regulatory Activities). Adverse events will be presented in two ways: (1) the number and proportion of participants experiencing at least one incidence of each event will be presented overall and by treatment group. The incidence of adverse events and serious adverse events by type will be compared between treatment arms using either Fisher's Exact mid-p-value or Chi-Square analysis as appropriate; and (2) a table displaying the total number of each event will be given overall and by treatment group. Listings of serious adverse events will be given, sorted by treatment, body system, and preferred term. Detail in these listings will include severity, relationship to study drug, and action taken as available.

2. Vital Signs

Repeated measures mixed models will be used to compare the treatment groups on blood pressure and heart rate from screening/baseline through study week 10.

3. The Hospital Anxiety and Depression Scale (HADS)

Repeated measures mixed models will be used to compare the treatment groups on depression and anxiety symptoms, as measured by the HADS, from screening/baseline through study week 10.

4. The Pittsburgh Sleep Quality Index (PSQI)

A repeated measures mixed model will be used to compare the treatment groups on the PSQI from screening/baseline through study week 10.

11.3.4 Missing Data

Logistic regression analyses will be conducted to identify patterns of attrition and to determine if there is differential attrition by treatment condition. A binary indicator variable for missing data will be regressed on treatment assignment and other covariates. Variables that are associated with attrition at or below the α =0.10 level of significance will be included in subsequent analyses where the assumption of data missing at random (conditional on covariates) is required.

For the primary outcome measure, whether (yes/no) a participant is stimulant-free during each week of the active treatment phase, missing data will be addressed as described in section 11.3.1. For the smoking outcome measures, missing smoking self-report/CO data will be treated as positive for smoking.

For all other outcome measures, and as a supplementary sensitivity analysis for the outcome measures above, a model to predict the existence of missing data based on the baseline covariates will be examined. Any baseline covariate that is related to the occurrence of missing data will be added to the list of control covariates for the hypothesis test. To minimize any impact of attrition on the test of hypotheses, intent-to-treat analyses will be conducted for all hypotheses. The GLMM analysis described in section 11.3.1 allows a missing at random assumption (Dang, Mazumdar and Houck, 2008). With these methods, if data are MAR, weeks with missing outcome may be ignored, and will therefore not be imputed. If the random effects model (GLMM) unexpectedly fails to converge, a general estimating equation (GEE) approach treating site as a fixed effect will be used. If this model is utilized, then missing data will be multiply imputed using standard multiple imputation procedures, since GEE inference is only valid if data are missing completely at random (MCAR).

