E16	Seek treatment for residential/inpt	Study Definition (outpatient stimulant dependence treatment)
E17	All stimulant-positive UDS results	Heavy users unlikely to complete study

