11.3.1 Primary Outcome

The primary hypothesis is that a significantly greater percentage of TAU+SCT, relative to TAU, participants will be stimulant-free during the weeks of the active treatment phase. For each participant, a stimulant-free week is defined as a week in which both urine samples test negative for stimulants and the participant self-reports no illicit stimulant use. A stimulant-positive week is defined as a week in which at least one urine sample tests positive for a stimulant or during which the participant self-reports illicit stimulant use. However, in the analysis of data from any clinical trial, strategies must be employed for handling missing data. In this trial, data for a week in which both urine samples are missing and the participant self-reports no illicit stimulant use will be treated as missing. For a week in which one stimulant-free UDS is produced, the second urine sample is missing, and the participant self-reports no illicit stimulant use or the self-report data are missing will be treated as negative (Table 6).

Data will be analyzed using a generalized linear mixed model (GLMM) for repeated-measures analysis (Brown and Prescott, 1999). Suppose Y represents the vector of observed response data, X and Z the fixed and random effects design matrices, and α and β be the vectors of fixed and random effects, respectively. Then, the GLMM model formulation assumes that

$$\mathrm{E}(\mathrm{Y}|\beta) = g^{-1}(\mathrm{X}\alpha + \mathrm{Z}\beta),$$

where $E(Y|\beta)$ is the expected value of Y conditional on the random effects vector, g^{-1} is the inverse link function, and $X\alpha + Z\beta$ is the linear predictor. The response variable Y will be modeled using the logit link function, i.e., $g(\mu) = \log(\mu / (1 - \mu))$. Fixed effects will include treatment group and week, while random effects will include site. SAS Proc GLIMMIX will be used to fit the model as follows:

proc glimmix; class site treatment; model Y = treatment week treatment*week / dist=binary link=logit covb solution; random intercept / subject=site; random _*residual_*/subject=patientid type=cs; run;

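### In the objective 6 analysis, participants of unknown smoking status are grouped with smokers, so part of any link between abstinence and stimulant use may reflect retention

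*Protocol*

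**What the plan says.** Protocol section 5.2, objective 6: "To evaluate whether achieving continuous smoking abstinence during study weeks 6-9 is associated with improved stimulant use outcomes". Item 11 of section 11.3.2 tests this with two groups. It will "compare the percentage of participants who achieve continuous smoking abstinence, relative to those who do not, on stimulant-free weeks" in study weeks 4-10, and it repeats the contrast for stimulant-free urine screens at 3 and 6 months.

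Two rules decide who counts as abstinent:

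- Section 6.5.2.2, item 3, requires no reported smoking on post-quit days 15-42 and no CO above 8 ppm, "AND at least one CO assessment per week". In practice that means at least four CO values, the first no later than day 23, and no gap above 13 days.
- Section 11.3.4 adds: "For the smoking outcome measures, missing smoking self-report/CO data will be treated as positive for smoking".

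The stimulant outcome follows a different rule. Under section 11.3.1, "data for a week in which both urine samples are missing and the participant self-reports no illicit stimulant use will be treated as missing", and under section 11.3.4 "weeks with missing outcome may be ignored, and will therefore not be imputed". Table 6 does score a week without urine as positive when use is reported.

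On who drops out, Table 1 justifies exclusion criterion 17 (all screening urines stimulant-positive) with "Heavy users unlikely to complete study".

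**The concern.** Counting missing data as smoking is a usual rule when smoking is the outcome compared between randomized arms. In item 11 smoking status defines the groups. An abstainer must have kept attending closely enough to meet the CO conditions. A non-abstainer is anyone who smoked and anyone who stopped attending.

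The two missing-data rules also pull apart. A participant who leaves is fixed as a non-abstainer, but the stimulant weeks after leaving are dropped. That person's earlier weeks, and any later week of reported use, count in the non-abstainer group. If people who use stimulants leave more often, that group looks worse partly because it holds the dropouts.

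At stake is the reading of objective 6: a positive result could not be told apart from a difference in retention. The 3- and 6-month contrasts are affected as well, through participants of unknown status who return for follow-up.

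**Working it through.** The protocol gives no figure for this analysis, so there is nothing to reproduce. All rates below are assumptions unless a section is named.

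**1. Apparent gap.** Assume 20% abstinent, 30% unknown, 50% observed smoking; 65% stimulant-free in both known groups and 45% among unknowns.

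- Non-abstainers as the plan forms them: (0.50 × 0.65 + 0.30 × 0.45) / 0.80 = 0.575.
- Apparent gap: 0.65 − 0.575 = 7.5 points.

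**2. Gap under true status.** Let q be the share of unknowns who were in fact abstinent, with the same 45% whether or not they smoked.

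- Abstainers: (0.20 × 0.65 + 0.30q × 0.45) / (0.20 + 0.30q)
- Smokers: (0.50 × 0.65 + 0.30(1 − q) × 0.45) / (0.50 + 0.30(1 − q))

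| q | Abstainers | Smokers | True gap (points) | Bias = 7.5 − true gap |
|---|---|---|---|---|
| 0% | 0.650 | 0.575 | 7.5 | 0 |
| 5% | 0.636 | 0.577 | 5.9 | 1.6 |
| 11% | 0.622 | 0.580 | 4.1 | 3.4 |
| 29% | 0.590 | 0.590 | 0 | 7.5 |

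The 29% row is the case where unknowns are abstinent as often as knowns: 0.20 / 0.70. The 5% and 11% rows borrow the follow-up and on-treatment abstinence rates that section 4.2.2 reports for an earlier network trial of the nicotine patch. They are a guide only, because that sample was mainly methadone-maintained and the rates do not describe dropouts.

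With 10% abstinent instead of 20%, the apparent gap is 0.65 − (0.60 × 0.65 + 0.30 × 0.45) / 0.90 = 6.7 points. The bias is then 2.8 points at q = 5% and 5.5 at q = 11%.

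**3. Weight of the unknowns.** Someone gone before week 4 has no observed urine result in weeks 4-10, and someone who never returns has no follow-up urine. If half of the unknowns are seen, the apparent gap falls to 0.65 − (0.325 + 0.15 × 0.45) / 0.65 = 4.6 points (4.0 with 10% abstinent). If one third are seen, it is 3.3 (2.9).

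**4. Does the mixed model protect?** A simulation used 528 participants, a mean stimulant-free rate of 0.65, within-person correlation 0.65 and weeks 4-10. True abstinence was 15-30% and independent of stimulant use. Dropout by week 9 was 20-40% and depended only on the previous observed stimulant result, so the stimulant outcome was missing at random by construction. There were 1000 runs per scenario.

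| Dropout hazard after a use week, relative to a free week | Odds ratio, abstainers vs others | Rejection rate at nominal 5% |
|---|---|---|
| 1 | 0.99-1.03 | 5-6% |
| 2 | 1.16-1.44 | 9-40% |
| 3 | 1.25-1.77 | 15-75% |
| Any, grouped by true status | 1.00-1.02 | 4.2-6.4% |

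Missingness at random for the outcome does not protect, because the error lies in the grouping. Like the 29% row, the simulation lets dropouts be abstinent as often as those who stay, so it marks the unfavourable end. If 30% of unobserved use weeks are later admitted and scored positive under Table 6, a small bias appears even at hazard ratio 1 (odds ratio 1.04-1.11).

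**The case against.** A reader might infer that the whole 7.5-point gap is spurious, or that the bias always favours abstinence when dropouts use more stimulants. The documents support neither. If the unknowns smoked, they belong in the comparator and the gap is a real association. Low abstinence among dropouts is plausible: half of the sample gets no study smoking treatment, and the cited rates are 5-11%. The direction is not fixed either. Suppose 11% of unknowns were abstinent and, unlike above, these were 65% stimulant-free. The true gap is then 0.65 − (0.46 − 0.033 × 0.65) / 0.767 = 7.8 points, slightly more than the apparent 7.5.

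The dropout link is also thinner than it looks. The Table 1 remark explains why one kind of candidate is excluded and does not quantify dropout among those enrolled. It makes the link plausible, no more. Candidates with some positive screening urines are still randomized and form a stratum (section 6.6).

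Partial safeguards exist. CO gaps of up to 13 days are tolerated, and predictors of attrition enter the models. Adjustment for covariates can absorb some of the bias, but it leaves the grouping unchanged.

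Finally, objective 6 is the last of six secondary objectives, non-randomized and worded as an association. That limits the stakes; it does not make a retention effect an answer to the question.

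**Conclusion.** The point holds as a limited one. Sections 6.5.2.2 and 11.3.4 together place unknown smoking status among the non-abstainers of item 11, and no planned analysis separates it. Bias needs two conditions: dropout related to stimulant use (or, to a small degree, the one-way scoring in Table 6), and some unknowns who did not smoke. It is about zero if either all unknowns smoked or dropout is unrelated to stimulant use with no later-admitted use.

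Under the illustrative 20% abstinent, 30% unknown and 65% against 45% stimulant-free, it is about 1.6 to 3.4 points if 5-11% of unknowns were abstinent. It reaches 7.5 only at 29%, and is smaller where unknowns contribute few weeks or no follow-up urine. These rates are assumptions. Section 4.2.1 cites completion of 19% and 15% in one cocaine trial, so 30% unknown is not extreme. This is a cheap improvement to a secondary analysis. It does not touch the primary analysis or the between-arm smoking comparisons.

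**What to change.** For item 11 only, derive a three-level smoking status:

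- abstinent: meets the section 6.5.2.2 definition;
- observed smoking: any self-reported smoking on post-quit days 15-42, or CO above 8 ppm on days 16-42;
- unknown: neither of these.

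Multiply impute the unknown status from observed TLFB, CO, stimulant results, arm, site and baseline data, and report the unknown group separately. The wording must cover the CO requirement in section 6.5.2.2 as well as the sentence in section 11.3.4; changing the latter alone leaves the grouping as it is.

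Show two sensitivity analyses: the present missing-equals-smoking grouping, and abstinent against observed smoking. The second should not be the main analysis, because it conditions on retention. In the worked example it gives 65 − 65 = 0 points, although the true gap is 5.9 when 5% of unknowns were abstinent. Read a positive objective 6 result as separate from retention only if the versions agree.

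Keep missing-equals-smoking for the between-arm smoking comparisons. The cost is one derived variable, one imputation model and a somewhat wider confidence interval for this analysis.
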